While bilirubin neurotoxicity with overt encephalopathy does occur, it is rare and currently unpredictable.¹¹ To improve our understanding of the relationship of UB to BAERs and NDI, we will request mothers who decline consent to randomize their infants to different Intralipid regimens to include their infants with those in the trial in an observational analysis relating their UB levels to their BAERs and neurodevelopmental findings (with and without adjustment for potential confounding variables).

We will also assess the clinical findings in all these infants in an effort to better understand their relationship to TSB and UB and the paradoxical findings reported by Oh and colleagues¹² that peak total bilirubin levels at 5 days age were inversely related to death or adverse neurodevelopmental outcomes in stable infants (a quite unexpected finding) although directly related to these outcomes in unstable infants (as expected). It is possible that because of bilirubin's antioxidant properties that higher TSB levels are protective in preventing death or from any cause providing the infants have not been exposed to factors that may predispose infants them to bilirubin neurotoxicity (e.g., sepsis, hypoxic ischemic episodes, severe acidosis, low albumin levels) and that the risk of bilirubin neurotoxicity with elevated TSB is over-estimated in these infants. Infants who were considered unstable in that study include all receiving mechanical ventilation at that age, and the need for mechanical ventilation at 5 days might simply be associated with factors that cause bilirubin neurotoxicity or that the need for mechanical ventilation is an effect of bilirubin neurotoxicity already present at that age. Informed consent will be obtained for each infant as approved by the IRB.

Hypotheses.

1. Among infants <27 weeks gestation or <750 g birth weight, the usual prescribed intralipid (**UL**) regimen and a reduced prescribed intralipid (**RL**) regimen (consisting of half the **UL** regimen) during the first two weeks after birth will result in somewhat higher mean unbound free fatty acids and mean UB values but similar BAERs, and in infants less than 27 weeks gestational age rates of death or impairment at 2 years postnatal age.

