Enrollment and Randomization. Patients will be approached for informed consent after informed consent has been given or refused for the NRN Cycled PT Trial. Infants for whom informed consent is obtained for this lipid study will be randomized using a variable block size stratified by study site and phototherapy use (continuous or cycled which may affect UB level) to either UL or RL using a web-based computerized program (REDCap). Lipid and phototherapy use are concurrent. Mothers who refuse consent infants for this lipid trial will be asked if they would consent for their infant to be included in the observational component of this study so that UB levels can be related to BAERs and 2-year outcomes. In the observational component Intralipid infusions will be at the attending physician's discretion and care would be altered only by collection of the small amount of blood (\leq 2 mL total) as for participants randomized to UL or RL.

Treatment Regimen.

UL regimen: Intralipid will be started at 1 g/kg/day and routinely advanced by 1 g/kg/day each day to a max of 3 g/kg/day as per usual clinical practice.

RL regimen: Intralipid will be started at 0.5 g/kg/day and routinely advanced by 0.5 g/kg/day each day to a max of 1.5 g/kg/day (half rate of usual clinical practice).

The assigned treatment regimen (UL or RL) will remain in effect for a minimum of 7 days and a maximum of 14. On postnatal day 8-14, the Intralipid preparation and dosage maybe changed at the discretion of the clinical team if phototherapy has been off for \geq 48 hours (TSB <5 mg/dL). (After that point, the Intralipid preparation and dosage maybe changed at the discretion of the clinical team). Throughout the study period, the infusion rates for both regimens may be decreased, and advances may be delayed for reason of lipid intolerance providing the justification is documented in the daily progress note. (Each study site should strive to standardize criteria for lipid intolerance so as to minimize the likelihood of using different criteria for the treatment groups). Intralipid infusions will be routinely initiated on specified day after the birthday as per the routine in the study site; this will be the first day after the birthday in Houston. The dates and times of start, stop, and changes in infusion rates will be recorded.

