Cointerventions. As appropriate for a pragmatic trial, the protein and glucose components of parenteral nutrition (**PN**) will be prescribed by the clinical team following usual care prescribing

guidelines and will likely differ between study groups. The quantities of macronutrients will be recorded during the intervention period (parenteral and enteral, g/kg/day).

Study Assessments. Blood samples for the study will be obtained with blood draws for clinical measurement of TSB levels such that the study will not require additional interventions for blood sampling. The first study blood sample will be obtained on the morning when the newborn is 4 days old (postnatal day 5). Age in days is defined as 0 days old at birth, and 1 day old at midnight on the birthday. Postnatal day 1 is until midnight of the birthday, and postnatal day 2 at midnight on the birthday, etc. Blood samples numbers 2-7 will be obtained on each subsequent morning through postnatal day 14 when a total bilirubin is obtained for clinical purposes as ordered by the clinical team. Bedside nurses collect blood using BD red-top microtainers at the same time that blood is sampled to measure total bilirubin for clinical purposes. A total of up to 6 study blood samples will be obtained within the first 2 weeks from birth, to not exceed total study blood volume of 2mL. (See sample schedule below).

Sample Number	Postnatal Day to Collect	Age (days)	Blood Volume*
*	1 (birthday)	0	0
*	2	1	0
*	3	2	0
1	4	3	0.25mL
2	5	4	0.25mL
3	6	5	0.25mL
4	7	6	0.25mL
5	8	7	0.25mL
6	9	8	0.25mL
Total Blood Vol.			<2 mL

*All samples will be 0.25mL with the exception of the morning after the lipid infusion is advanced to the peak infusion rate (usual group 3 g/kg/day or reduced group 1.5g/kg/day). On this day ONLY, the blood sample volume will be 0.5mL.

Blood Volume and Measurements.

A 0.5 ml will be obtained on the morning after the lipid infusion has been advanced to the peak infusion rate (1.5 or 3.0 g/kg/d).

The priority for measurements for 0.5 ml sample will be:

1. UB [10ul serum] in duplicate [20 ul serum]
2. Albumin [10ul serum] in duplicate [20 ul serum]
3. Unbound FFA complete (60ul serum) in duplicate (120ul serum)

This includes FFA blended estimate

On other days, 0.25 ml blood will be obtained each morning (up to 6 samples).

The priority for measurements for the 0.25 ml samples will be:

1. UB [10ul serum] in duplicate [20 ul serum]
2. Albumin in duplicate [10ul serum] in duplicate [20 ul serum]

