Data Analysis. Intention-to-treat analyses will be performed under the supervision of [name]. Generalized linear mixed models will be performed to analyze all outcomes and will include treatment group, PT type (continuous and cycled), as covariates with random effects for study site. Interaction will be assessed for treatment group and PT type. Bayesian analyses will be performed in evaluating differences in treatment effects overall and in different patient subgroups and centers. For the primary outcome and any other continuous outcome, a linear regression model will be used. Binary outcomes will be analyzed with a logistic regression and count data with a Poisson or negative binomial regression model. All priors will be neutral. For binary outcomes, all priors will be centered at RR of 1.0 (indicative of no difference between treatment groups with a 95% prior interval of 0.3-3.0 (in the log RR scale a Normal distribution with mean of 0 and variance of 0.50). A Normal (0,10²) prior will be used for the intercept term and Normal (0,1) for all other variables in the model. For the standard deviation of the center random effect, a half-Normal (0,1) prior will be used. Similar neutral informative priors (based on previous NRN PT trial⁹ where possible) will be used for non-binary outcomes. We will report posterior medians and 95% credible intervals for group differences and relative risks. We will also report posterior probability of benefit/harm for each outcome.

Similar analyses will be conducted for the cohort analyses (including infants in the observational arm).

Data Interpretation. If UB is higher and BAER wave V latency is longer in the UL than the RL group, the findings would likely prompt changes to more conservative use of Intralipid use in the

first 1-2 weeks after birth in extremely preterm infants. If values for UB and BAER wave V latency in the UL group are no higher than the RL group, the findings would support continue use of the UL regimen to provide somewhat greater caloric intake. If UB is higher with no discernible effect on wave V latency, the findings would suggest that the UB level were not high enough to cause bilirubin neurotoxicity with effects lasting to 34-36 weeks. However, findings at 2 years would need to be scrutinized for evidence of adverse neurodevelopmental effects.

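### The half-dose contrast is assured for about one week, not the two weeks stated in Hypothesis 1, and the UB and uFFA outcomes have no time window that separates the two periods

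*Combined protocol and SAP*

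**What the plan says.** Hypotheses, item 1, defines RL as half the UL regimen and predicts that the two regimens "during the first two weeks after birth will result in somewhat higher mean unbound free fatty acids and mean UB values but similar BAERs".

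Treatment Regimen gives the schedules. For UL: "Intralipid will be started at 1 g/kg/day and routinely advanced by 1 g/kg/day each day to a max of 3 g/kg/day". For RL: "Intralipid will be started at 0.5 g/kg/day and routinely advanced by 0.5 g/kg/day each day to a max of 1.5 g/kg/day". It then sets the duration: "The assigned treatment regimen (UL or RL) will remain in effect for a minimum of 7 days and a maximum of 14". Release within that range is conditional: "On postnatal day 8-14, the Intralipid preparation and dosage maybe changed at the discretion of the clinical team if phototherapy has been off for" at least 48 hours, with TSB below 5 mg/dL given in parentheses. Reductions and delayed advances for lipid intolerance are allowed throughout. The times of infusion starts, stops and rate changes are recorded.

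Study Assessments puts the first sample on postnatal day 5 and continues: "Blood samples numbers 2-7 will be obtained on each subsequent morning through postnatal day 14", on mornings when a clinical TSB is drawn. It also caps the number of samples at 6. The table beneath it instead places samples 1 to 6 on postnatal days 4 to 9.

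Outcome Measures lists the UB area above 40 nM/L (primary), and mean UB, proportion above 40, peak UB, and uFFA area, mean and peak (secondary). None has a start or end day. Data Analysis specifies intention to treat, with treatment group and phototherapy (PT) type as covariates, and adds: "Interaction will be assessed for treatment group and PT type". It has no rule for samples taken after an infant is released from the assigned regimen.

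**The concern.** The hypothesis and the treatment rule describe different contrasts. The hypothesis has a half-dose difference lasting two weeks. The rule has one that lasts at least 7 days and then continues, or not, according to phototherapy status, TSB and clinical judgement. After release an RL infant may receive more lipid, or an infant in either group may change preparation. A sample drawn then need not reflect a half-dose difference.

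If such samples are pooled with the earlier ones, a small difference in mean UB or mean uFFA has two possible readings: lipid dose has little effect, or the doses had stopped differing. Data Interpretation would count UB and wave V latency that are no higher under UL as support for continuing UL, so the distinction matters.

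The release condition also depends on events after randomisation that belong to the bilirubin pathway. It could be met at different rates by assigned group or by PT type, so the length of the lipid contrast may vary with both.

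**Working it through.** **Inputs.** The two schedules and the 7-14 day duration come from Treatment Regimen. So does the Houston start on the first day after the birthday, which is postnatal day 2 under the day-numbering in Study Assessments. Sample days come from the Study Assessments prose and table. No intolerance reductions are assumed.

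**1. The plan's own figure.** Cumulative lipid, days 2-14:
- UL: 1 + 2 + 3×11 = 36 g/kg
- RL: 0.5 + 1 + 1.5×11 = 18 g/kg
- Ratio 18/36 = 0.50

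So half reproduces if both regimens run to day 14.

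**2. The assured part of the contrast.**
- Through day 7: UL 1 + 2 + 3×4 = 15; RL 0.5 + 1 + 1.5×4 = 7.5; difference 7.5 of 18 g/kg (42%).
- Through day 8: UL 18; RL 9; difference 9 of 18 g/kg (50%).

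The second line applies if the 7 days run from first infusion on day 2. The text does not say whether they run from birth or from first infusion.

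**3. What release could do to the dose contrast.** Let f be the fraction of RL infants released on day 8 and moved at once to the UL maximum, with UL unchanged. This is an assumption; the documents give no value for f and do not say what change would be made.
- Days 8-14 ratio = 10.5(1 + f)/21
- Days 2-14 ratio = (18 + 10.5f)/36

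| f | Days 8-14 ratio | Days 2-14 ratio |
|---|---|---|
| 0 | 0.50 | 0.50 |
| 0.5 | 0.75 | 0.65 |
| 1 | 1.00 | 0.79 |

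If release starts on day 9, f = 1 gives (1.5 + 18)/21 = 0.93 and 27/36 = 0.75.

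**4. Samples that can reflect a released dose.** A dose changed during day 8 first shows in the morning sample of day 9.
- Table (days 4-9): day 9 only, 1 of 6.
- Prose, daily from day 5, capped at 6 (days 5-10): days 9 and 10, 2 of 6.
- Prose, seven samples as its numbering implies (days 5-11): 3 of 7.
- Sparse draws, for example every second day from day 5 (days 5, 7, 9, 11, 13; an assumption): 3 of 5.

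If the day 8 sample is also counted as exposed, the first three become 2 of 6, 3 of 6 and 4 of 7.

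**5. Effect on each type of summary.** Suppose the group difference is d in every sample under assigned doses and zero in released infants' later samples. With m of n samples exposed, the difference in means is d(1 − f·m/n). As f runs from 0 to 1, the loss is 0 to 17% by the table (m/n = 1/6) and 0 to 33% by the prose with daily draws (2/6). This is a range over an unknown f under a strong assumption, not an estimate.

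The UB area above 40 nM/L behaves differently. It accumulates, so equal contributions after release leave the absolute difference already built up intact. Only the difference that might have accrued later is forgone. Released infants also have TSB below 5 mg/dL, which may leave little area above the threshold to add.

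**The case against.** The strongest reply is that the trial compares prescribed regimens, and Treatment Regimen defines those as lasting 7 to 14 days with conditional release. Intention to treat compares these policies validly, and Rationale and Data Interpretation already speak of the first 1-2 weeks. Infusion changes are recorded and prescribed fat is compared by group, so achieved separation will be visible. A cut at day 8 also discards week-2 data from infants still on their assigned dose. All of this stands. It is why the all-sample analysis should be kept and the fixed-window analysis placed beside it. It does not supply a window for UB and uFFA, or align Hypothesis 1 with the rule.

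Several stronger readings are tempting but unsupported:
- A reader might infer that clinicians are free to change lipid from day 8. They are not: phototherapy must have been off for at least 48 hours, so a day 8 change needs it stopped by about day 6.
- A reader might take the 0.75-0.79 cumulative ratio as the trial's contrast. It is the worst case for a single released infant.
- Sampling to day 14 might suggest that most samples are exposed. The cap of 6 and a first sample on day 4 or 5 limit this, and later sampling depends on clinical TSB draws.
- A reader might infer that the planned treatment-by-PT interaction is confounded with exposure time. That is possible, but nothing in the documents shows that release differs by PT type.

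**Conclusion.** The point holds as a mismatch between the stated contrast and the assured one, together with a missing outcome window. The half-dose contrast is assured for about the first week, which carries 42% to 50% of the planned cumulative dose difference given a Houston start and no intolerance reductions. After that it depends on a post-randomisation condition. Mean UB, the proportion above 40 nM/L and uFFA may include samples taken after release: 1 of 6 by the table, 2 of 6 by the prose with daily draws, more if draws are sparse. The primary UB area is much less exposed.

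The actual dilution cannot be stated, because the documents give neither a release rate nor the change that would follow. A reader might go further and conclude that the intention-to-treat comparison is invalid or that no contrast remains in week 2. The documents do not support either: the comparison is valid for the 7-14 day policy, and infants who do not meet the release condition stay on their assigned regimen. What is at stake is whether a small UB or uFFA difference can be told apart from lost dose separation.

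**What to change.** Leave the release rule unchanged and keep the all-sample intention-to-treat analysis. Then:

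1. Pre-specify beside it a comparison by assigned group of UB (area, mean, peak, proportion above 40 nM/L) and uFFA (area, mean, peak) in one fixed window for all infants, ending with the morning sample of postnatal day 8.
2. Use the recorded infusion-change times to confirm that this sample precedes any change. The check is needed because a postnatal day begins at midnight and changes are permitted on day 8.
3. Do not cut at each infant's own release; its timing depends on bilirubin and phototherapy, so the cut would be informative.
4. Assess the treatment-by-PT interaction in the same window.
5. Reconcile Hypothesis 1 with Treatment Regimen: the contrast is assured for about the first week and variable after that. State whether the 7 days run from birth or from first infusion.
6. Reconcile the sampling prose with the table on first day, last day and number of samples.

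The cost is some rewording and one extra analysis of data already being collected, with no change in care. The downside is fewer samples per infant in the fixed window: 5 of 6 are retained by the table (days 4-8), and 4 of 6 by the prose with daily draws (days 5-8).

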**Bilirubin Neurotoxicity (BN) and Neurodevelopmental Impairment (NDI) in
Extremely Preterm (EP) Infants: Avoidable by Reducing the Usual Intravenous Lipid
(UL) Administration?**

NCT04584983

Version Date: 07/28/2023

Bilirubin Neurotoxicity (**BN**) and Neurodevelopmental Impairment (**NDI**) in Extremely Preterm (**EP**) Infants: Avoidable by Reducing the Usual Intravenous Lipid (**UL**) Administration?

[name], [name], MSc, MPH, [name], [name], [name], [name], [name], and [name], MPH

Rationale. Extremely premature infants have very limited caloric reserves. Because of the pressing need to at least meet maintenance caloric requirements, early aggressive parenteral nutrition with glucose, protein, and lipids has been recommended for preterm infants, particularly those born before 27-28 wks.¹ Intralipid, the most commonly used parenteral fat preparation, is commonly initiated starting 1-2 days after birth. However, the optimal age for administration is unclear as the most recent systematic review of the Cochrane Collaboration found no statistically significant benefits of “early” administration of lipids (<5 days after birth) from later introduction.² Whether a relatively high caloric intake from lipids is better than a relatively low intake is also unclear. The dose of Intralipid is commonly increased from 1 g/kg/d on the day that it is started to 2 g/kg/d on the following day to 3 g/kg/d on the next day. The dose is usually limited to a maximum of 3 g/kg/d, partly to avoid potential dose-related adverse effects including chronic lung disease, increase in pulmonary vascular resistance, impaired pulmonary gas diffusion, sepsis, free radical stress and bilirubin neurotoxicity.

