3. Unbound FFA blended estimate [5ul serum] (#1)
4. Unbound FFA complete [60ul serum] (#1)
5. Unbound FFA blended estimate [5ul serum] (#2)
6. Unbound FFA complete [60ul serum] (#2)

The nurse or person obtaining blood for routine TSB levels will collect whole blood at the same time in study-provided red-top microtainer and immediately place the microtainer in a pre-

labeled amber plastic bag provided by the research team. The amber bag containing the sample will be placed in the specified location in the research refrigerator (4 degrees Celcius) as soon as feasible. A member of research team will pick up the specimen within 12 hours, transport the specimen to the UT-Houston McGovern Medical School. In the laboratory space at UT Houston McGovern Medical School, a centrifuge will be used to separate serum which will be labeled and frozen at minus 80 degrees Celsius until samples are shipped in batch to Fluoresprobe Sciences in San Diego, California.

Measurands in each whole blood sample will include concentrations of UB, albumin, total unbound free fatty acids (**uFFA**), and a uFFA profile, which includes concentrations of specific uFFA. These results will not be available with the bedside clinician and will not affect direct patient care. These will be linked with any of the following measurands from the same blood sample measured in the hospital laboratory: TSB, indirect bilirubin, direct bilirubin, albumin, triglyceride, glucose, serum bicarbonate. Additionally, if a blood gas is obtained within 4 hours of this blood draw, the pH from that blood gas will be linked to the sample, providing no intervening ventilator changes were made prior to the blood draw. Other data reflecting general status and severity of illness and/or potentially influencing UB levels will be abstracted from the medical record, including baseline variables such as sex, gestation, anthropometrics, multiple gestation, delivery information, Apgar scores, SNAP-II scores, Z scores at birth, 28 days of life, and 36 weeks postmenstrual age, etc.

Data Management. Data will be entered and stored in a secure UTH REDCap database. Paper logs of data will be secured in a locked cabinet or room.

Outcome Measures. To be compared by treatment group:

Primary outcomes:

- Area under the UB curb with UB concentration >40 nM/L
- BAER wave V latency at 34-36 weeks post menstrual age (or as soon as feasible if the infants if an artifact free BAER cannot be obtained at 34-36 weeks)

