Secondary outcomes:

- Mean UB concentration and proportion of measurements >40 nM/L, peak UB
- Peak UB concentration
- Area under the total unbound FFA (**uFFA**) concentration – time curve; mean FFAu and peak uFFA
- Peak total serum bilirubin (TSB)
- Direct bilirubin > 1.5 mg/dL before discharge
- Macronutrients prescribed (parenteral and enteral protein, fat and carbohydrate, g/kg/day)
- Weight change (g/kg/day) and Z score change from birth through day 28 and at 36 weeks postnatal age
- Relevant data abstracted from the medical record and stored in the existing databases:
 - Serial FiO₂ and ventilator settings (routinely collected generic data)
 - Bronchopulmonary dysplasia (oxygen requirement at 36 weeks PMA)
 - Perinatal and hospital acquired sepsis episodes
 - Other clinical findings potentially related to signs of or susceptibility to bilirubin neurotoxicity
 - Death or NDI as assessed at 24 months PMA
 - Death or hearing loss at 24 months PMA
 - Death or cerebral palsy at 24 months PMA

Cohort analyses (across study groups and any infants in the observational arm) Associations of interest will include:

- UB and death or NDI, unadjusted and adjusted for potential confounders
- UB and wave V latency, unadjusted and adjusted for potential confounders
- Wave V latency and death or NDI, unadjusted and adjusted for potential confounders
- uFFA measured by single probe and total uFFA measured as the sum of individual uFFA
- uFFA and UB
- Total uFFA and individual uFFA(s)

Power and Sample Size. We plan to study sufficient infants at UTH to assess BAERs in 40 infants in each treatment group and have more than 80% power at $P < 0.05$ to identify a difference between groups in wave V latency longer than 0.3 millisecond ($SD = 0.5$ millisecond). This sample size would also afford sufficient power to assess a clinically important difference in UB level.

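### Wave V latency can be recorded across 34-36 weeks PMA or later, but age at test is not in the treatment model; adding it is a cheap gain in precision

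*Combined protocol and SAP*

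**What the plan says.** Outcome Measures lists two primary outcomes. The second is "BAER wave V latency at 34-36 weeks post menstrual age (or as soon as feasible if the infants if an artifact free BAER"; the line goes on to allow for infants without a usable trace at that age. The fallback sets no upper age limit.

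Data Analysis describes one model family for all outcomes, which "will include treatment group, PT type (continuous and cycled), as covariates with random effects for study site", and adds a check of the treatment-by-phototherapy interaction. It then states: "For the primary outcome and any other continuous outcome, a linear regression model will be used". PMA at test is not named, latency is not standardised for age, and no analysis is restricted to tests done in the window. A prior is given for other model variables, but none is named.

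Outcome Measures does foresee adjustment for potential confounders, but only in the cohort analyses, and it does not list them. Randomisation does not address the matter either: infants are "randomized using a variable block size stratified by study site and phototherapy use".

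Power and Sample Size plans to "assess BAERs in 40 infants in each treatment group" and claims that this will "have more than 80% power at $P < 0.05$ to identify a difference between groups". The target is a difference in "wave V latency longer than 0.3 millisecond ($SD = 0.5$ millisecond"). It does not say whether that SD already contains variation in age at test. A later paragraph raises enrolment to 175.

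**The concern.** The outcome is an absolute latency in milliseconds, and the planned comparison treats a trace taken at 34 weeks and one taken at 38 weeks as equivalent. If latency falls with maturation, part of the spread between infants is simply age at test. Left out of the model, it goes into the residual and widens the interval for the treatment effect.

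This matters because Data Interpretation gives meaning to the absence of a difference. Higher UB without a discernible latency effect would suggest that UB was not high enough to do harm lasting to 34-36 weeks, and UB and latency no higher under the usual regimen would support continuing it. The protocol also expects similar BAERs in the two arms. Avoidable noise therefore pushes toward the expected answer. In addition, a trace taken well after 36 weeks is weak evidence for a statement about 34-36 weeks, whatever the rate of maturation.

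**Working it through.** **Inputs from the documents.** 40 infants per arm with BAER, difference 0.3 ms, SD 0.5 ms, P < 0.05 (sidedness not stated), power above 80%; enlarged enrolment 175, so at most about 87 per arm (the number with a BAER is not given).

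**Assumptions, not in the documents.** Latency shortens by b = 0.05 to 0.2 ms per week of PMA. In-window tests are spread evenly over 34 0/7 to 36 6/7 weeks. In the late-test scenarios, 10% of infants are tested after the window.

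**1. The plan's own figure.** Power ≈ Φ(0.3 / (SD × √(2/n)) − 1.96). With SD 0.5 and n = 40, the standard error is 0.5 × √(2/40) = 0.112 ms, and two-sided power is 76.5% (75.5% by the noncentral t). One-sided power is 85.0%. The stated figure above 80% is thus reached only one-sided; two-sided, 44 per arm are needed. At 87 per arm, two-sided power is 97.7%.

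**2. Spread of PMA at test.**
- Window only: variance 3²/12 = 0.75, SD 0.87 weeks.
- 10% spread evenly over 37-42 weeks: the two groups have means 35.5 and 39.5, overall mean 35.9. Variance = 0.9 × (0.75 + 0.4²) + 0.1 × (5²/12 + 3.6²) = 2.32, SD 1.52 weeks.
- 10% spread evenly over 37-39 weeks: means 35.5 and 38, overall 35.75. Variance = 0.9 × (0.75 + 0.25²) + 0.1 × (2²/12 + 2.25²) = 1.27, SD 1.13 weeks.

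**3. Share of the stated variance.** Share = b² × Var(PMA) / 0.25.

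| Timing of tests | b = 0.05 | b = 0.1 | b = 0.2 |
|---|---|---|---|
| All in window | 0.75% | 3% | 12% |
| 10% at 37-39 weeks | 1.3% | 5.1% | 20% |
| 10% at 37-42 weeks | 2.3% | 9.3% | 37% |

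For example, 0.2² × 0.75 / 0.25 = 12%.

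**4. Effect on two-sided power for 0.3 ms.** There are two readings of the 0.5 ms.

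*It excludes age spread.* Omitting PMA raises the SD to √(0.25 + b² × Var(PMA)).
- Window only: SD 0.502 to 0.529; power 76.2% to 71.7% at 40 per arm, 97.6% to 96.2% at 87.
- 10% at 37-42 weeks: SD 0.506 to 0.586; power 75.6% to 63.0% at 40 per arm, 97.5% to 92.2% at 87.

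*It includes age spread.* Adjusting for PMA lowers the SD to √(0.25 − b² × Var(PMA)).
- Window only: SD 0.498 to 0.469; power rises from 76.5% to between 76.8% and 81.6% at 40 per arm.
- 10% at 37-42 weeks: SD 0.494 to 0.396; power rises to between 77.5% and 92.3%.

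**5. Bias, if timing differed by arm.** Bias = b × difference in mean PMA at test. If one arm had 10 percentage points more late tests, each 4 weeks later than a typical in-window test (39.5 against 35.5), the shift would be 0.10 × 4 × b = 0.02 to 0.08 ms. That is 7-27% of the 0.3 ms target and below the standard error of 0.112 ms at 40 per arm. If mean test age is the same in both arms, the shift is zero.

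**The case against.** **The size rests on outside assumptions.** This stands. No section gives a rate of maturation or a distribution of test ages. At 0.05 ms per week with all tests in the window, the age share is under 1% of the variance and the power cost is under one point.

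**The fallback means the earliest usable date, not any later age.** This also stands. Spreading late tests to 42 weeks is a pessimistic reading. Stopping at 39 weeks roughly halves the share, to 1.3-20%.

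**The planned SD may already contain age spread.** It may. Power would then not fall below plan, and adjustment would be purely a gain. The recommendation is the same.

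**The enlarged sample absorbs the loss.** Largely so, if BAER numbers approach 87 per arm: power stays at 92% or more in the scenarios above. The loss matters more near 40 per arm.

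**A null result is not the last word.** Data Interpretation says that the 2-year findings would then need scrutiny. That limits the consequence but does not make the latency estimate more precise.

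**A stronger reading that a reader might infer.** The Rationale says that the usual dose is capped "partly to avoid potential dose-related adverse effects including chronic lung disease". One could reason that the usual-lipid arm would have more infants on prolonged respiratory support, hence more late and more mature traces, hence a masked prolongation. The documents do not support that chain: nothing links respiratory support to artifact or delayed testing, and nothing predicts a difference in timing between arms. It is a reason to report timing by arm, not evidence of bias.

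**An upper age limit would do harm.** Correct, if it governed the primary analysis. It would remove randomised infants because of something that happened after randomisation, against the intention-to-treat principle stated in Data Analysis and with a risk of selection. An in-window restriction belongs in a sensitivity analysis only.

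**Conclusion.** The point holds as a cheap improvement. It rests on two features of the text: the test age has no upper bound, and the treatment model omits age at test. Provided that latency shortens with maturation, the omission leaves removable variance in a primary outcome: about 1-12% of 0.25 ms² from the window alone, and about 2-37% if 10% of infants are tested at 37-42 weeks, for assumed slopes of 0.05-0.2 ms per week. The first range takes the window to run to 36 6/7 weeks; if it ends at 36 0/7, the variance is 2²/12 = 0.33 and the share 0.3-5%. The omission is certain, but its size is not.

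It should not be read as showing that the wave V comparison is biased or that a lipid effect will be hidden. Test ages with the same distribution in both arms cost precision only.

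**What to change.** In Data Analysis, add exact PMA (weeks and days) at the BAER as a prespecified covariate in the wave V model for the randomised comparison, with a prior for its coefficient. In the cohort analyses involving wave V latency, name PMA at test among the confounders.

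Keep every randomised infant with a usable trace in the primary analysis, whatever the age at test. Add a sensitivity analysis limited to tests at 34-36 weeks, saying whether the window ends at 36 0/7 or 36 6/7. Report the distribution of PMA at test and the number of late tests by arm.

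The cost is a few sentences, with no new visits or procedures. Gestation is already among the abstracted variables. The documents do not list the BAER date as a recorded item, so it must be captured. One drawback remains: PMA at test is measured after randomisation and could in principle be affected by treatment, so the unadjusted estimate should be shown beside the adjusted one.
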